## **Process Evaluation**

## Implementation

Timely access to care: the percentage of patients with hip or knee pain who are assessed within 48 hours of calling for an appointment will be reported descriptively and compared between arms by calculating relative risks with robust Poisson regression, using GEE-type covariance estimators to account for clustering, assuming an exchangeable working correlation matrix. Empirical covariance (“sandwich”) bias-adjusted (residual-based) estimators and the Fay and Graubard correction will be used. We will incorporate the same covariates as with our effectiveness analysis.

First contact care by the PT: the percentage of patients with hip or knee pain in the PT-led primary care arm who visited a PT as their first point of contact for the current episode of hip or knee pain will be reported descriptively.

Hip and knee pain management provided: the proportion of patient participants who receive the following will be reported descriptively: education; exercises; psychological interventions; referrals to internal primary care team members; referrals to external HCPs; medications prescribed, deprescribed, and suggested; diagnostic imaging ordered; notes to employers or insurers; messages sent between internal primary care team members. Comparison between arms will be made using robust Poisson regression. Comparison between arms will be made using relative risks and confidence intervals using GEE-type covariance estimators, accounting for clustering, and assuming an exchangeable working correlation matrix. Empirical covariance (“sandwich”) bias-adjusted (residual-based) estimators and the Fay and Graubard correction to account for small number of clusters will be used.

Patient adherence to recommendations: adherence to PT activity and exercise as reported at 6-week follow-up will be reported descriptively. The proportion of people accessing PT in the community will be reported descriptively and compared using robust Poisson regression, accounting for clustering.

## Potential Mechanisms

If the intervention is effective (i.e., The PT-led primary care model results in greater patient functioning than the usual care group), we will carry out mediation analyses to assess potential mechanisms. Specifically, we will assess whether changes in self-efficacy (PSEQ) or changes in psychosocial risk factors (PHQ-2, PCS, TSK-11) explain or partially explain changes in patient functioning (LEFS score). We will conduct a separate mediation analysis for each potential variable (PSEQ, PHQ-2, PCS, TSK-11). We will use a stepped approach proposed by Beril and colleagues to investigate temporal and dynamic trends of the treatment effect across repeated measures using theoretical insights about the mediation effect to choose the appropriate mediation model. The intervention effect explained by the mediator (indirect effect) will be calculated as the difference between the total effect (the effect calculated in the primary analysis) of the PT-led primary care model on the LEFS score and the direct effect of the intervention. We will evaluate the possibility of mediation using the significance of this effect. We will use the LEFS outcome at the 12-month follow-up timepoint as the outcome variable. This analysis will provide effect measures that allow us to report the proportion of the total effect that is mediated through each of the potential mediator variables.. Our causal/associated conceptual model has considered, and controlled for where needed, mediation analysis assumptions that there is no intervention-outcome, mediator-outcome, or intervention-mediator confounding or mediator-outcome confounding that is influenced by the intervention itself. To explore potential mechanisms of cost differences in our cost analysis, we will report the proportion of cost differences between arms that are healthcare utilization costs and the proportion of costs associated with missed occupational activities.

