**Inclusion/Exclusion:** All adult ( $\geq 19$  years) patients who sought primary care for their hip or knee pain of any duration at participating sites were invited to meet with the RA to discuss participating in the study. Potential participants were excluded if: they reported not being able to understand, read, and write English; they had known cancer causing their hip or knee pain; or they reported being unable to complete the scheduled follow-up surveys over the one-year study period. The inclusion criteria for primary care sites were to have at least 1,500 rostered patients and two or more family physicians. Those sites that already had physiotherapy services or not enough space to include the physiotherapist were excluded.

**Study Power:** Participants were recruited over a 13-month period at all 14 primary care sites (7 PT-led arm, 7 usual care arm). Our power calculation is based on methods described by Hemming et al. Our sample size calculation is targeted to detect a clinically meaningful mean difference of 9 points on the Lower Extremity Functional Scale (LEFS) using a two-sided alpha of 0.05, assuming a conservative standard deviation of 16, a conservative intracluster correlation coefficient of 0.1, a cluster autocorrelation coefficient of 0.5, an individual autocorrelation coefficient of 0.6, and a coefficient of variation of 0.7. Allowing for an attrition of 20% of patient participants at the 12-month follow-up, we require a sample size of 560 participants to achieve  $>80\%$  power. Pilot work for this study suggested we would recruit 1 patient per week per site; as such, we planned and prepared resources to recruit approximately 728 participants.

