**Data Analysis Plan**

All analyses will be by intention to treat principle. Descriptive statistics will be provided for baseline characteristics and outcomes using means (standard deviation) or medians (interquartile range) for continuous variables and frequencies (percent) for categorical variables. We will compare arms using linear mixed models and generalized estimating equations (GEE) to account for clustering and present the corresponding p-values. Analyses will be performed using SAS, version 9.4 (SAS Institute Inc; Cary, NC).

The estimand for patient health outcomes will be the time-specific patient participant treatment effect, adjusting for clustering by primary care site. The primary outcome (LEFS) will be analyzed using linear mixed regression with restricted maximum likelihood (REML) estimates under the assumption of Missing at Random (MAR), which will allow the use of all available data without the need for multiple imputation. The Kenward-Rogers degrees of freedom correction will be used to account for a small number of clusters. The 12-month timepoint will provide the intervention effect as the adjusted least square mean difference between arms with 95% confidence intervals. Secondary comparisons will be made using adjusted least square mean differences between arms at all intermediate time-points. Fixed effects in the mixed model will include time, intervention group by time interaction (omitting the group main effect), pre-specified covariates associated with hip and knee function (patient participant age, sex, duration of current episode of hip or knee pain, income, highest level of education, and comorbidity score), and primary care site rurality and number of active patients (the covariates from the covariate-constrained allocation procedure). Repeated measures will be modeled using a covariance structure determined by information criteria (AIC/BIC). Clinic site will be included as a random effect to account for site clustering. We will assess for potential risk of bias associated with missing data by comparing the characteristics of those who participated. We plan to carry out a sensitivity analysis for a potential departure of our MAR assumption using a delta-adjusted imputation pattern mixture model approach. This approach will allow us to investigate the robustness of our trial outcomes with regard to the missing values of the LEFS.

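### The indirect effect subtracts a direct effect from the primary-analysis total effect, and nothing requires the two to share participants, covariates or missing-data handling

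*Combined protocol and SAP*

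**What the plan says.** The Potential Mechanisms section of the combined protocol and SAP gives a rule for the indirect effect. It is "calculated as the difference between the total effect (the effect calculated in the primary analysis", minus the direct effect of the intervention. The same section then adds:

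- on the outcome: "We will use the LEFS outcome at the 12-month follow-up timepoint as the outcome variable";
- on inference: "We will evaluate the possibility of mediation using the significance of this effect";
- on reporting: the analysis will "report the proportion of the total effect that is mediated" through each of four mediators (PSEQ, PHQ-2, PCS, TSK-11), taken one at a time;
- on the model: a stepped approach over the repeated measures will be used "to choose the appropriate mediation model".

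The Data Analysis Plan defines the primary analysis that supplies the total effect. It is a REML mixed model for repeated LEFS, fitted "under the assumption of Missing at Random (MAR), which will allow the use of all available data without the need for multiple imputation". It has arm-by-time terms but no main effect of arm, which holds the arms equal at baseline. Baseline LEFS is not in the covariate list and enters only through the repeated-measures structure.

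For the direct effect the plan gives no model, analysis set, covariate list, rule for missing mediators or interval method. The mean imputation described elsewhere fills missing items within a survey, not missing surveys. The delta-adjusted sensitivity analysis concerns missing LEFS values and does not extend to the mediators or the indirect effect.

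**The concern.** The difference method isolates mediation when the total and direct effects differ only by inclusion of the mediator. Here one term is fixed as the primary estimate, which draws on every wave and on people with no 12-month LEFS, and the other term is left open. If they also differ in who is analysed, in adjustment or in missing-data handling, that difference is absorbed into the indirect effect, its test and the proportion mediated.

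Table 1 shows LEFS and all four mediators collected at the same surveys. A gap due to missing surveys would therefore be similar for every mediator, and could look like consistent evidence for or against all four mechanisms. The mechanisms paper is one of the planned publications.

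**Working it through.** **1. The plan's own figure.** The plan gives no figure for the mediation analysis, so the only figure to reproduce is the sample size behind the primary effect. It is set by "Allowing for an attrition of 20% of patient participants at the 12-month follow-up".

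- 14 sites x 32 analysed = 448, and 448 / 0.80 = 560.
- Design effect with coefficient of variation 0.7 and ICC 0.1: 1 + ((1 + 0.49) x 32 - 1) x 0.1 = 5.67.
- Correlation of site means over time: r = (32 x 0.1 x 0.5 + 0.9 x 0.6) / (1 + 31 x 0.1) = 2.14 / 4.1 = 0.52, so 1 - r² = 0.73.
- SE = sqrt(2 x 16² / 224 x 5.67 x 0.73) = 3.07, and 9 / 3.07 - 1.96 = 0.97, giving power 0.834.

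The stated power above 80% is reproduced. A t reference on 12 df gives 0.768 under this formula. A generalised least squares version with baseline plus one follow-up gives 0.912 (normal) and 0.860 (t). None of this bears on the present point.

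**2. How many people are at issue.** At 20% attrition, 0.20 x 560 = 112 participants (0.20 x 728 = about 146 at the planned recruitment) could inform the total effect but not a 12-month completer model.

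**3. Decomposition.** Let T(primary) be the primary estimate, D the direct effect, and T(matched) the total effect from the same sample and covariates as D. Then

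indirect (plan) = [T(matched) - D] + [T(primary) - T(matched)].

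The second bracket contains no mediator. It is zero in expectation only if both totals estimate the same quantity.

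**4. Size of the second bracket, if D is a completer estimate.** This is a simulation of 1,500 runs per scenario.

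- From the plan: 14 sites, SD 16, ICC 0.1, cluster autocorrelation 0.5, individual autocorrelation 0.6, 12-month effect 9. There were 40 participants per site (560 / 14).
- Assumed: earlier arm effects of 4, 6 and 8 points; a mediator shifted by arm but with no effect on LEFS, so the true indirect effect is 0; loss of the 12-month survey depending on 9-month LEFS (logistic, slope 1 per SD). In the opposite-mechanism case, low scorers leave the PT-led arm and high scorers leave usual care.
- Total effect: baseline-constrained repeated-measures likelihood on everyone. Direct effect: 12-month completers, adjusted for the mediator.

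Results at 20% dropout, in LEFS points, mean (SD):

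| Dropout | Total | Plan's rule, D adjusted for baseline LEFS | Share of total | Plan's rule, D without baseline LEFS | Matched sample and covariates |
|---|---|---|---|---|---|
| Random | 8.90 | 0.01 (0.37) | 0.1% | -0.01 (1.84) | -0.01 (0.25) |
| Same mechanism in both arms | 9.18 | 0.21 (0.39) | 2.3% | 0.47 (1.77) | 0.00 (0.25) |
| Opposite mechanisms by arm | 9.01 | -1.35 (0.43) | -15.0% | -3.16 (1.90) | 0.00 (0.25) |

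The simulation error of a mean is small: 0.43 / sqrt(1,500) = 0.011. Over 10% to 30% dropout, the baseline-adjusted column runs from 0.11 to 0.27 (same mechanism) and from -0.70 to -2.00, or -7.8% to -22.5% of the total (opposite mechanisms).

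**5. Adjustment matters even without informative dropout.** If the direct model reuses the primary covariate list, which lacks baseline LEFS, the false indirect effect under random dropout has SD 1.84 against 0.25 when matched, a ratio of 1.84 / 0.25 = 7.4.

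**6. Cross-checks, without site clustering.**

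- A separate simulation (n = 560, 18-21% dropout) gave 0.02, 0.18 and -1.26 for the same three mechanisms, against about 0.0 for matched or joint estimation. With a true indirect effect of 3, the mismatched subtraction returned 1.70 against 2.98.
- A milder arm difference (dropout depending on 3-month LEFS more strongly in one arm, about 20-23%) gave -0.4 to -0.7 with no true mediation, and 2.25 to 2.6 when the truth was 3.

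**The case against.** A reader might infer that the plan takes its two effects from different participants, so that missing-data differences will be counted as mediation. The documents do not support that.

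- **Completers are an inference.** No direct-effect model or analysis set is stated. A stepped approach over repeated measures is compatible with a longitudinal model on all participants. Naming 12-month LEFS as the outcome does not imply completers, since the primary effect is also read at 12 months from a model using every wave. The method is deferred to citations numbered 137 onward, while the reference list ends at 78, so it cannot be checked there. This stands.
- **Two models are not a fault in themselves.** The difference method always fits one with and one without the mediator. This stands.
- **Identical rows are sufficient, not necessary.** A total and a direct effect that are both valid under missing at random also recover the indirect effect. In simulation (n = 560, 17-25% dropout, 600 runs, no clustering) this gave -0.03 to 0.02 when the truth was 0, and 2.98 to 3.04 when it was 3. This stands.
- **Size and sign are assumed.** The documents give no dropout mechanism, and 20% is a planning allowance. The larger errors need dropout that differs by arm, and those simulated are negative, so they mask mediation. No error rate was computed for the significance test. This stands.
- **The consequences are limited.** The analysis belongs to the process evaluation, runs only if the intervention is effective, and uses mediators from the same surveys as LEFS, which narrows the mismatch. It does not remove it, because the primary model also uses people without 12-month LEFS.

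What survives is that the subtraction is a stated rule, not merely an omission, and that no other section aligns its two terms.

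**Conclusion.** The point holds in conditional form. The plan fixes the total effect as the primary estimate and does not require the direct effect to match it in participants, covariates or missing-data handling. Differences other than the mediator can therefore enter the indirect effect, its test and the proportion mediated.

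If the direct effect is a completer estimate and dropout is about 20%, the error is about zero under random dropout, about 0.2 LEFS points when dropout works alike in both arms, and about -1.3 of 9 points when it runs in opposite directions. The last case is deliberately strong, and a milder arm difference gave -0.4 to -0.7. The error can hide or create mediation. Separately, leaving baseline LEFS out of the direct model alone adds substantial noise. All sizes rest on assumed dropout mechanisms. Only this conditional secondary analysis is affected, but the correction is cheap enough that it should be made.

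**What to change.** Amend Potential Mechanisms to state, for each mediator, that total, direct and indirect effects will be estimated in one prespecified analysis set, with identical covariates (including baseline LEFS), identical treatment of site clustering and identical missing-data handling, differing only by the mediator. State the rule for missing mediators. Give the indirect effect an interval from that same analysis that accounts for the 14 sites. Report the primary-analysis effect beside these estimates, not inside the subtraction.

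The preferred route is to model or impute mediator and LEFS jointly under missing at random. Refitting the total effect among completers is a fallback only. It removes the false indirect effect when there is no mediation, but with a true indirect effect of 3 it gave 2.65 to 3.59 under LEFS-dependent dropout, with completer totals of 8.3 to 11.7 against a true 9. Under strong same-mechanism dropout it erred about as much as the mismatched subtraction (2.65 against 3.31).

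The cost is a sentence or two of SAP wording and one additional fit per mediator, with somewhat more work for the joint route. The total in the mediation table may differ slightly from the headline estimate and will need a footnote. At the version date the analysis was to begin only after data collection ended, so the change could be made in advance.

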## Patient Experiences

We will explore the experiences of patient participants with hip or knee pain who have participated in the PT-led primary care model for hip or knee pain using in-depth qualitative interviews conducted and analyzed in an interpretive description tradition. Interpretive description is a qualitative approach that is founded on naturalistic inquiry and involves focusing on identifying applied and clinically relevant themes that can inform healthcare or health service delivery. Interpretive description, therefore, is well suited to helping us achieve our process evaluation goal to understand experiences and perspectives with the PT-led primary care model for people with hip or knee pain. The experiences and perspectives of patients are expected to lead to refinements how the model of care is implemented if effective. Strategies to support rigour will include use of two independent coders for the first two to three manuscripts to ensure reliability and consistency in coding, use of reflexive journaling and reflexive dialogue amongst team members throughout the analytic process, incorporation of detailed field notes and written memos, long and deep engagement with the qualitative interview data, and maintaining an audit trail to document the analytic decisions throughout the research process.

## Ethics

Ethics approval for this study has been obtained from the Queen's University Health Science and Affiliated Teaching Hospitals Research Ethics Board (HSREB #6040471). Written consent was obtained from all participants willing to participate.

**Discussion:** The results of this pragmatic trial and accompanying mixed methods process evaluation will provide comprehensive evidence to guide health system leaders and primary care teams regarding the implementation of a new PT-led primary care model of hip and knee pain in Ontario, with relevance for health systems across Canada and around the world. Our approach combines quantitative analyses of patient health outcomes and healthcare costs with in-depth qualitative inquiries into how the model of care was experienced and implemented. This design allows us not only to assess effectiveness and cost implications, but also to understand contextual factors, barriers, and facilitators that shape real-world uptake. The evaluation has been co-developed with knowledge users—including individuals living with hip and knee pain and health care professionals engaged in the intervention—to ensure that study outcomes are meaningful and aligned with current health system priorities.

We will share out findings through peer-reviewed manuscripts on: the effectiveness of the PT-led primary care model for people seeking primary care with hip or knee pain, the cost-effectiveness of the model, how the model of care was implemented (including differences in care provided between arms), potential mechanisms (if the intervention is effective) and the experiences of patients.

**Acknowledgements:** Not applicable.

## Funding

This study protocol was supported by Canadian Institutes of Health Research (CIHR) Institute of Musculoskeletal Health and Arthritis (grant reference number 185253) and the Arthritis Society of Canada (agreement number 02360-00). Neither funder took part in the writing of this protocol and analysis plan.

## Competing Interest

The authors declare that they have no competing interests, including: no support from any organization for this work, no financial relationships with any organizations that might have an interest in our study

in the previous three years, no other relationships or activities that could appear to have influenced this work.

## **Data Availability**

For access to the data, please contact the corresponding author.

## **Abbreviations:**

CCI: Canadian Classification of Health Interventions

ED: Emergency Department

EHR: Electronic health record

GEE: Generalized estimating equation

GROC: global rating of change

HCP: healthcare provider

LEFS: Lower Extremity Functional Scale

MAR: Missing at random

MRC: Medical Research Council (UK)

MSK: musculoskeletal

NPRS: Numeric Pain Rating Scale

OA: Osteoarthritis

OHIP: Ontario Health Insurance Program

PSEQ: Pain Self-Efficacy Questionnaire

PT: Physiotherapist

QALY: Quality-adjusted life years

RA: Research assistant

REDCap: Research Electronic Data Capture

REML: Restricted maximum likelihood

RCT: Randomized controlled trial

